## ABBREVIATIONS AND DEFINITIONS OF TERMS

Abbreviation	Definition
ASL	American Sign Language
RSA	Respiratory Sinus Arrhythmia
T1	Time 1
T2	Time 2
T3	Time 3
BMI	Body Mass Index
SES	Socio-economic status
RCFCS	Responsiveness to Child Feeding Cues Scale
NDS-R	Nutrition Data System for Research
CEBQ-T	Child Eating Behavior Questionnaire-Toddler
IFSQ	Infant Feeding Styles Questionnaire
IBQR	Revised Infant Behavior Questionnaire
NGSE	New Generalized Self-Efficacy Scale
IIQ	Infant Intentionality Questionnaire
PHQ-4	Patient Health Questionnaire-4
PI	Principal Investigator
Co-I	Co-Investigator
IRB	Institutional Review Board
ECG	Electrocardiogram
IBI	Interbeat Interval
REDCap	Research Electronic Data Capture
UNC	The University of North Carolina at Chapel Hill
CTSA	Clinical and Translational Science Awards Program
FTP	File Transfer Protocol
ITS	Information Technology Services
WIC	The Special Supplemental Nutrition Program for Women, Infants, and Children

## PROTOCOL SYNOPSIS

Study Title	Enhancing Caregiver-Infant Communication to Prevent Obesity
Funder	Eunice Kennedy Shriver National Institute of Child Health and Human Development
Clinical Phase	Stage 1 for Behavioral Intervention Development
Study Rationale	
Once obese as an infant, the relative risk of remaining obese appears to rise with increasing age. Thus, the early years of life have been posited as an important target period for obesity prevention. Widely viewed as a response to genetic, interpersonal, and environmental factors, obesity fundamentally reflects an imbalance between energy intake and expenditure. Self-regulation of energy intake aligned with physiologic need is essential to this balance. The process(es) by which infants begin to disassociate eating behavior from physiologic need is unclear, thus it is crucial to better understand predictors of individual differences in self-regulation of energy intake.
 
A chronic mismatch between a caregiver's feeding behavior and the infant's state (feeding in the absence of hunger and/or feeding beyond fullness), is thought to contribute to obesity by undermining the infant's capacity to self-regulate intake; the current proposal will be the first to examine the effects on autonomic regulation.

Study Objective(s)	
Primary Outcome
 
To evaluate the initial impact of the intervention. We expect the following for the experimental group:
 
Infants will have more optimal growth (weight-for-length Z scores closer to 50th %) than the control group by T3.
 
Secondary Outcome
 
To evaluate the initial impact of the intervention. We expect the following for the experimental group:
 

○ Infants will have enhanced self-regulation of energy intake (closer to estimated energy requirements) than the control group by T3.

 
Tertiary Outcomes
 
To evaluate the initial impact of the intervention. We expect the following for the experimental group:
 

○ A) Dyads will demonstrate (1) improvement in observed feeding responsiveness and (2) higher observed feeding responsiveness than the control group by T3 (6-months post-baseline).

○ B) Mothers will (1) perceive higher infant satiety responsiveness and (2) report more responsiveness

---

feeding behaviors and beliefs than the control group by T3.

Evaluate the feasibility and acceptability (e.g., burden) of the intervention and study methods including recruitment, enrollment, and data collection (self-report, anthropometrics, video observations, and respiratory sinus arrhythmia [RSA]) for infants and their mothers.

**Exploratory Outcome**

- Explore preliminary data on concordance between dyadic feeding interactions and autonomic regulation in both mothers and infants (RSA). We expect higher observed dyadic feeding responsiveness to be associated with larger change scores in RSA (enhanced self-regulation) for both mother and infant.

---

**Test Article(s)**  
(If Applicable)

N / A

---

**Study Design**

Two-group randomized repeated measures design.

---

**Subject Population**

**key criteria for  
Inclusion and Exclusion:**

Inclusion Criteria

1. Subjects age 3 months to 50 years.
2. Mothers must be able to read, understand, and speak English or Spanish and be willing to be randomized and participate in data collection. Those who are randomized into the experimental group must also be willing to learn ASL specific to communication of hunger, thirst, and fullness.

Exclusion Criteria

1. Dyads will be excluded if infants:
  - a. were born more than 6 weeks earlier than their estimated due date,
  - b. have any developmental delays or disabilities that make it difficult for them to eat, drink, or communicate,
  - c. attend regular daycare,
  - d. or will be younger than 4 months or older than 9 months at the time of the first ASL training.

---

**Number of Subjects**

160

---

**Study Duration**

Each subject's participation will last between 6-6.5 months depending on how long it takes to schedule the last dietary recalls. The entire study is expected to last 2 years.

---

**Study Phases**  
**Screening**

Screening: screening for eligibility and obtaining consent

---

Study Treatment Follow-Up	Study Treatment: study intervention/experimental treatment from baseline visit (T1) monthly until 3-months post-baseline (T2) Follow-up: 6-months post-baseline (T3)
Efficacy Evaluations	Primary efficacy evaluation measures: 
 
1. Infants in the intervention group will have more optimal growth (weight-for-length Z scores closer to 50th %) than the control group by T3.
 

Pharmacokinetic Evaluations	N/A
Safety Evaluations	
 
• Assessment of self-reported health of parent and infant prior to data collection
 
• Monitoring of parent's and infant's responses during intervention and data collection
 
• Reports of adverse events
 

Statistical And Analytic Plan	To evaluate the initial impact of the intervention longitudinally for each maternal and infant outcome listed in the primary, secondary, and first two tertiary outcomes above, we will fit separate linear mixed-effects random coefficients models. These will model the linear trajectories of the group-specific means across all available time points using the actually observed timing. The initial impact of the intervention will be formally assessed through a statistical hypothesis test of model parameter representing the difference in these slopes. More specifically, these models will include terms for the intervention group (as an indicator variable), actual time of data collection (as continuous weeks from baseline), and their interaction. Covariates identified above to correct for imbalance will be included, as well as the factors stratified in the randomization, and the models will account for the repeated measures correlation structure. Statistical contrasts will also be constructed to estimate and test the changes over time separate for each group.
DATA AND SAFETY MONITORING PLAN	Study personnel will be on-site in subjects' homes for the duration of data collection and will monitor the response of subjects during data collection. Should any concerns arise during data collection, they will be addressed immediately by study personnel and the PI and Co-I will be notified as soon as possible if they are not on site. Though unlikely, should any concerns arise after data collection, subjects will be given the PI's contact information to share their concerns and the PI will address concerns directly or through appropriate referrals. Any concerns that arise over the course of the study will be recorded and aggregated as part of the feasibility data and shared with the research team and the IRB as necessary.

# **1 BACKGROUND AND RATIONALE**

## **1.1 Introduction**

Once obese as an infant, the relative risk of remaining obese appears to rise with increasing age. Thus, the early years of life have been posited as an important target period for obesity prevention. Widely viewed as a response to genetic, interpersonal, and environmental factors, obesity fundamentally reflects an imbalance between energy intake and expenditure. Self-regulation of energy intake aligned with physiologic need is essential to this balance. The process(es) by which infants begin to disassociate eating behavior from physiologic need is unclear, thus it is crucial to better understand predictors of individual differences in self-regulation of energy intake. It is well established that autonomic regulation may support infant behavioral regulation, suggesting that autonomic function may be a critical area to consider here. Moreover, self-regulation is strongly influenced by dyadic interaction quality during infancy, and findings reveal that more responsive interactions are associated with more effective autonomic regulation. A chronic mismatch between a caregiver's feeding behavior and the infant's state (feeding in the absence of hunger and/or feeding beyond fullness), is thought to contribute to obesity by undermining the infant's capacity to self-regulate intake; the current proposal will be the first to examine the effects on autonomic regulation.

We propose an intervention to enrich the capacity of mother-infant dyads to perform their respective interactive tasks. We plan to teach mothers American Sign Language (ASL) signs indicative of hunger, thirst, and satiety, which they will in turn teach their preverbal infant. This training in ASL will be augmented with targeted information for mothers about infants' capacities to self-regulate energy intake in response to hunger and satiety and communicate those states with intention. Mothers also will be taught about expected development of infants' eating behaviors and nutritional requirements to support healthy growth.

Using a two-group randomized repeated measures design, this study aims to 1) evaluate the feasibility and acceptability of the intervention and study methods, including recruitment, enrollment, and data collection (self-report, anthropometrics, video observations, and respiratory sinus arrhythmia [RSA]) for infants and their mothers; 2) evaluate the initial impact of the intervention on infant growth and nutritional intake, observed feeding interactions, and reported infant feeding behaviors and maternal feeding behaviors/beliefs; and, 3) explore preliminary data on concordance between dyadic feeding interactions and autonomic regulation in both mothers and infants (RSA). In addition to a variety of self-report and anthropometric measures, this study will use integrated behavioral (video) and physiologic (RSA) measures to better understand feeding dynamics and their relationship with obesity risk. Understanding these processes is essential for developing appropriate preventions, or interventions, that will help reduce the prevalence of early childhood obesity and its extension into later childhood and beyond.

The study's interventions and data collection will take place in participants' homes.

## **1.2 Name and Description of Investigational Product or Intervention**

We propose an intervention to enrich the capacity of mother-infant dyads to perform their respective interactive tasks. We plan to teach mothers American Sign Language (ASL) signs indicative of hunger, thirst, and satiety, which they will in turn teach their preverbal infant. This training in ASL will be augmented with targeted information for mothers about infants' capacities to self-regulate energy intake in response to hunger and satiety and communicate those states with intention. Mothers also will be taught about expected development of infants' eating behaviors and nutritional requirements to support healthy growth.

## **1.3 Non-Clinical and Clinical Study Findings**

Nearly 10% of U.S. infants were obese in 2009-2010. Given increased relative risk of remaining obese later in life and poor health consequences of childhood obesity during childhood and adulthood,

obesity prevention during infancy has become a priority for research. Research in this area is relatively new and results have been mixed regarding measures of obesity. Obesity intervention components have included: teaching caregivers strategies for improving infant sleep quality/duration, increasing infant physical activity, providing nutritional education to support breastfeeding, increasing food variety, appropriate timing of complementary food introduction, and increased responsiveness to infant hunger and satiety cues. These studies report improvements in several factors that have been associated with obesity risk, including: improved infant sleep, less TV exposure, decreased sweet/juice intake, delayed introduction of solids, increased breastfeeding duration and/or rates, and increased parental responsiveness (self-reported) to infant hunger and satiety cues. Most studies have failed to impact significantly body mass index (BMI) or Weight/Length. Two have found a decrease in either weight for length % or BMI while two other studies have noted an increase in weight and length or BMI. While impact on BMI or Weight/Length appears equivocal, it is quite possible that effects on obesity status and growth will become evident later in development; most of the studies reported outcomes < 6 months after delivery of the last intervention component. Of importance regarding safety, none of the intervention studies demonstrated concerning weight loss or growth delay. While the etiology of obesity is considered multifactorial, it arises fundamentally through an imbalance in energy intake and output. The aforementioned studies used multi-focal intervention components, yet there was little focus on the assessment of support for energy intake self-regulation and no focus on evidence of self-regulation (eating behavior responsive to physiologic state [i.e., hungry or satiated]). Several studies included efforts to increase caregiver responsiveness to infant hunger and satiety cues, which is thought to support self-regulation, yet only one investigative team has reported improvement in parental responsiveness (self-reported). In short-term protocols (meal to meal), infants have demonstrated the ability to self-regulate energy intake over days and weeks, through compensation or adjustment for variations in the energy content of food. This self-regulatory capacity appears to increasingly diminish in the years following toddlerhood, at least in short-term protocols. Thus, it has been suggested that the first 2 years of life may be a critical period for the development of self-regulation of intake.

There is strong evidence in the extant literature that social, emotional, and cognitive self-regulation can be nurtured or derailed within the caregiver-infant relationship; evidence among older children

[figure not shown]

Figure 1. Feeding Responsiveness & Obesity

suggests that self-regulation of energy intake may be influenced by the caregiving environment, too. This is an integral component of our theoretical orientation, which is guided by a model linking feeding responsiveness to obesity (Figure 1). For our study, this model is situated within the larger relational developmental systems paradigm^34, in which the biological, psychological, and sociocultural systems interpenetrate and mutually influence one another over the course of development. This paradigm requires us to acknowledge that energy intake self-regulation is modifiable by relational developmental processes. Thus, we examine this phenomenon across multiple levels in order to understand its development and consider how interventions may affect it.

Although self-regulation is most easily assessed by observable behavioral patterns, it is critical to understand the psychobiological processes that support these behaviors. One of the most studied correlates of behavioral self-regulation is within the autonomic nervous system, more specifically vagal tone, which is often assessed through respiratory sinus arrhythmia (RSA). Baseline cardiac patterns are considered to be a neurophysiological mechanism underlying autonomic and behavioral reactivity. Although RSA is relatively stable during a calm and restful state, it is sensitive to environmental demands and thus extant research also measures change in RSA from baseline to an external challenge.

The ability to effectively reduce RSA during challenge, followed by a return to baseline levels, may be an adaptive process allowing participation in demanding tasks by shifting attention from internal homeostatic demands to external ones to support the use of coping strategies to control affective or behavioral arousal. Withdrawal of RSA (larger RSA change scores) during a challenging situation has been related to better emotion regulation in infants and caregivers.

Thus far, most studies of infant and toddler self-regulation of eating have focused on the contributions of temperament (e.g., attention spans, soothability, negative reaction to food). Findings have revealed an association between these characteristics at 1 year of age and larger weight increases over time and obesity at 6 years of age. To our knowledge, only one study has looked at the autonomic correlates of these behaviors, and found that older children (5.5 years old) who demonstrated lower levels of RSA withdrawal (a purported indicator of less regulation) during lab stressors were significantly more likely to be overweight five years later, but this was only true among African-American children. This finding was unclear, but the authors suggested, “future research should examine whether individual differences in cardiac regulation relate to observable differences in children’s eating behavior”(p. 1824).

In adults, obesity has been related to low baseline RSA and smaller RSA change during a stressor. Increased vagal control in adult dieters could be a physiological endophenotype of successful eating self-regulation. Findings revealed that dieting success (i.e., self-control of food intake) was associated with increased parasympathetic control, even after controlling for BMI, smoking, alcohol, and exercise. We propose an innovative assessment of the development of parasympathetic function during feeding interactions earlier in life to better understand the direction of this effect. We are particularly interested in exploring patterns of infant and maternal RSA change in relation to infant and maternal behaviors during feeding, as an index of engagement and early regulation of food intake. This is particularly relevant in light of global and particularly energy intake development of self-regulation in infancy and toddlerhood.

Our proposed linkage of dyadic feeding responsiveness and autonomic regulation (RSA) with indicators of enhanced energy intake self-regulation, optimal growth, and adiposity addresses the call for obesity prevention efforts focused on the bidirectional, mutually responsive orientation between parent and child. The study will be the first systematic assessment of a well-established communication system (ASL) to enhance dyadic communication between infants and their caregivers specific to feeding. The study acknowledges the caregiver and infant as each having a responsibility during feeding and moves beyond a focus on the caregiver to both partners, equipping them with new ways of communicating and perceiving one another during feeding. We propose to use ASL as it has been shown to facilitate communication, parental perception of infants’ capacity to communicate with intent, and caregiver responsiveness with hearing infants. Our focus on hunger, thirst, and satiety signs should not overwhelm the dyad. The public health impact could be profound if the intervention is found to be promising.

While this is an exploratory/developmental study, we do acknowledge the existing literature on additional characteristics that may affect mutual responsiveness between infant and caregiver. These include infant characteristics (temperament) and caregiver characteristics (education, socio-economic status (SES), prior parenting experience, depression and anxiety, perception of infant intention, and parenting self-efficacy). Therefore, we plan to assess the feasibility of measuring these characteristics as part of planning for our larger future study of biopsychosocial systems and their role in obesity risk in infancy and early childhood.

## **2 STUDY OBJECTIVE**

### **2.1 Primary Objective**

To evaluate the initial impact of the intervention. We expect the following for the experimental group:

- Infants will have more optimal growth (weight-for-length Z scores closer to 50th %) than the control group by T3.

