### **2.2 Secondary Objective**

To evaluate the initial impact of the intervention. We expect the following for the experimental group:

- Infants will have enhanced self-regulation of energy intake (closer to estimated energy requirements) than the control group by T3.

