## 5 STUDY EVALUATIONS AND MEASUREMENTS

Variables and Their Measurement	Measure	Data Source	T1	T2	T3	Alpha
Aims 1: Feasibility & Acceptability	Screening and Enrollment logs	Project Manager	X			
	Field Notes	RA's	X	X	X	
	Exit Interview	Mothers			X	
Aims 2 & 3						
Dyadic Feeding Responsiveness						
Mutual Responsiveness during	Responsiveness to Child Feeding Cues Scale (RCFCS) 	Infants & Mothers	X	X	X	0.85-0.94

Feeding						
Infant Eating Behavior						
Dietary Intake	Nutrition Data System for Research (NDS-R)	Mothers	X	X	X	
Eating Behavior	Child Eating Behavior Questionnaire-Toddler (CEBQ-T) 	Mothers	X	X	X	0.65-0.87
Infant Anthropometry						
Growth	Weight-for-length% & Z score	Infants	X	X	X	
Maternal Feeding Behavior/Beliefs	Infant Feeding Styles Questionnaire (IFSQ) 	Mothers	X	X	X	0.75-0.94 b
Autonomic Regulation	Respiratory Sinus Arrhythmia (RSA)	Infants & Mothers	X	X	X	
Additional Characteristics						
Infant						
Temperament	Revised Infant Behavior Questionnaire (IBQR) 	Mothers	X	X	X	0.91-0.92
Sex, Birthweight, & Gestational Age	Demographics	Mothers	X			
Maternal						
Parental Self-Efficacy	New Generalized Self-Efficacy Scale (NGSE) 	Mothers	X	X	X	0.85-0.88
Perception of Infant Intentionality	Infant Intentionality Questionnaire (IIQ) 	Mothers	X	X	X	0.77-0.87
Depression & Anxiety	Patient Health Questionnaire-4 (PHQ-4) 	Mothers	X	X	X	0.82
Demographic Characteristics	Demographics & Pregnancy History	Mothers	X			

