### **6.3 Statistical Methods**

Descriptive statistics will be calculated for each measure (see Aims 2 & 3 in Table of Measures, Section 5) at each time point by group. All analyses will be conducted using an intention-to-treat approach.

Preliminary analyses will be conducted to determine whether, despite randomization, the intervention and control groups exhibit a random imbalance at baseline on any measured variable. If important imbalances are found, the corresponding variable will be considered as a covariate in subsequent models to statistically correct for the imbalance. To evaluate the initial impact of the intervention longitudinally for each maternal and infant outcome listed above as primary, secondary, and the first two tertiary outcomes (i.e., more optimal growth, indicators of enhanced self-regulation of energy intake [NDS-R data compared to age- and sex-specific estimated energy requirements], reported infant feeding behavior and maternal feeding behaviors/beliefs, and observed dyadic feeding responsiveness), we will fit separate linear mixed-effects models. These could include a random coefficients model to examine the linear trajectories of the group-specific means across all available time points using the actually observed timing. The initial impact of the intervention will be formally assessed through a statistical hypothesis test of model parameter representing the difference in these slopes. More specifically, these models will include terms for the intervention group (as an indicator variable), actual time of data collection (as continuous weeks from baseline), and their interaction. An alternative modeling strategy would be to utilize mixed-effects model in a repeated measures context to examine the trajectories of the group-specific means across all available time points using the visit timepoint; these models will include terms for the intervention group (as an indicator variable), visit timepoint (as one or more indicators to reflect this categorical variable), and their interaction term(s). In this scenario, the initial impact of the intervention will be formally assessed through a statistical hypothesis test of linear contrasts of model parameters representing the between-group difference at each timepoint. Covariates identified above to correct for imbalance will be considered for inclusion in these models, as well as the factors stratified in the randomization, and the models will account for the repeated measures correlation structure. Statistical contrasts will also be constructed to estimate and test the changes over time separately for each intervention group. As useful information for planning subsequent studies, effect sizes for each measure will be calculated for each follow-up time point as the ratio of the mean difference between the intervention and the control groups to its standard deviation, as well as the producing the estimated correlation matrices across the repeated measures.

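### The primary hypothesis concerns distance from the median, but the plan defines no distance response and no success direction; read by default as mean signed Z, the test does not match the hypothesis

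*Combined protocol and SAP*

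**What the plan says.** Section 2.1 states the primary objective as "Infants will have more optimal growth (weight-for-length Z scores closer to 50th %) than the control group by T3". The Protocol Synopsis repeats it under the objectives and under the efficacy evaluations. Section 2.2 frames the secondary objective in the same way: "Infants will have enhanced self-regulation of energy intake (closer to estimated energy requirements) than the control group by T3".

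The measures table in Section 5 gives the growth variable as "Weight-for-length% & Z score", collected at T1, T2 and T3.

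Section 6.3 names the responses only by label ("i.e., more optimal growth, indicators of enhanced self-regulation of energy intake"). One option there is a random coefficients model to "examine the linear trajectories of the group-specific means across all available time points using the actually observed timing", with the intervention effect assessed by a "statistical hypothesis test of model parameter representing the difference in these slopes". The other option treats visit as categorical and tests between-group differences at each visit. The Synopsis gives only the slope version: "These will model the linear trajectories of the group-specific means across all available time points using the actually observed timing". For intake, Section 6.3 says "NDS-R data compared to age- and sex-specific estimated energy requirements" and does not say how the comparison is formed.

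Section 6.4 bases power on a linear difference of .4 SD by T3, with 32 dyads per group, AR(1) correlation 0.9 and one-sided .05, and claims more than .86. It does not say whether the .4 SD is on a signed or a distance scale, or which direction counts as benefit.

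**The concern.** Being closer to the 50th percentile means having a smaller |Z|. A mean of signed Z cannot measure that: infants rising from below the median cancel infants falling from above it. A mean percentile has the same property. The eligibility criteria in Section 3.4 contain no weight criterion and recruitment is from the community, so infants on both sides of the median should be expected.

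Two errors are possible if signed Z is the response. Real convergence can leave the group mean unchanged and be reported as no effect. A general downward shift can be reported as benefit even though infants have, on average, moved away from the target. And if the response is simply left open, the analyst can choose among percentile, signed Z and |Z| after seeing the data, and these can point in different directions.

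**Working it through.** **Inputs from the documents.** 40 dyads per arm (Section 3.3); 20% attrition, so 32 per arm; AR(1) with ρ = 0.9; difference .4 SD by T3; one-sided .05 (all Section 6.4). With visits at 0, 3 and 6 months the T1–T3 correlation is 0.9² = 0.81.

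**Assumptions.** Z is normal with SD 1. The documents give no baseline distribution, so the starting mean is varied.

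**Step 1: the plan's own power.** Power = Φ(δ/SE − 1.645), with SE = s·√(2/32).
- Change from T1 to T3: s = √(2(1 − 0.81)) = 0.616, SE = 0.154, 0.4/0.154 = 2.60, power .83.
- Baseline-adjusted: s = √(1 − 0.81²) = 0.586, SE = 0.147, 0.4/0.147 = 2.73, power .861.

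The stated figure reproduces with baseline adjustment. It also reproduces (.866) for an unadjusted slope that adds the 8 dyads per arm assumed lost, with T1 and T2 data only.

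**Step 2: true convergence.** Every intervention infant is pulled 30% toward Z = 0 by T3 and controls are unchanged. From a starting mean of 0, mean |Z| falls from 0.80 to 0.56. Rejection rates for the T1–T3 change contrast (simulation, at least 20,000 trials per row):

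| Starting mean Z | Signed Z, test for lower | \|Z\|, test for lower |
|---|---|---|
| 0 | 5% | 59% |
| +0.3 | 15% | 62% |
| +0.5 | 25% | 66% |

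At mean 0 the signed test rejects at its type I error rate. Adjusting for baseline raises the |Z| figure at mean 0 to 74% and leaves the signed figure at 5%. With no effect, the |Z| test rejects 4.9%, so skewness of |Z| does not disturb the level at this sample size.

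**Step 3: uniform downward shift of 0.4.** Here lower Z is counted as success, which the documents do not say. For Z ~ N(m, 1), E|Z| = √(2/π)·exp(−m²/2) + m(1 − 2Φ(−m)).

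| Starting mean | Mean \|Z\| without shift | Mean \|Z\| with shift | Signed test calls success |
|---|---|---|---|
| −0.3 | 0.83 | 0.99 | 82–83% |
| 0 | 0.80 | 0.86 | 82% |
| +0.2 | 0.81 | 0.81 | 82% |
| +0.5 | 0.90 | 0.80 | 82% |

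E|Z| is symmetric in m, so a shift of −0.4 breaks even when it carries the mean from +0.2 to −0.2. Below +0.2 the signed success contradicts the objective; above +0.2 it agrees with it.

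**Step 4: power on the |Z| scale.** For bivariate normal Z with mean 0 and correlation r, corr(|Z₁|,|Z₂|) = [√(1 − r²) + r·arcsin(r) − 1] / (π/2 − 1). At r = 0.81 this is 0.615. For 0.4 SD of |Z| with 32 per arm:
- Change: s = √(2(1 − 0.615)) = 0.877, SE = 0.219, ratio 1.82, power .57.
- Baseline-adjusted: s = √(1 − 0.615²) = 0.788, SE = 0.197, ratio 2.03, power .65.

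Holding .86 would need 72 or 58 completers per arm, that is 72/0.8 = 90 or 58/0.8 = 72.5, rounded up to 73, randomized per arm, against 40 planned.

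**The case against.** The strongest reply is that no section names signed Z as the response. Section 6.3 refers to the outcome as defined in the objectives, and a model for group means can be fitted to a deviation score as well as to Z. The measures table lists raw measures rather than analysis variables: dietary intake appears there only as the recall software, while Section 6.3 analyses a comparison with requirement. This stands. A reader might infer that the plan commits to testing signed Z, and the documents do not go that far. Signed Z is the default when the listed variable is put into the listed model.

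A reader might also infer that the plan will label movement away from the median as success. That needs a success direction, which is nowhere given; the one-sided level appears only in the power section. The effect also reverses above a starting mean of about +0.2, and the baseline mean is unknown. The by-visit descriptive statistics would show a group mean falling below zero.

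Nor is it shown that the secondary outcome has the same fault. Section 6.3 leaves open whether intake is compared with requirement by difference, ratio or absolute deviation. What is shown there is a gap in definition.

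Finally, the simulation uses a T1–T3 contrast among completers, while the plan is a three-visit mixed model that also uses incomplete data. That would change the percentages somewhat, but not the cancellation. The developmental stage of the study tempers the consequence, but this is still the named primary outcome.

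**Conclusion.** The concern holds in this form: the response variable and success direction for the primary outcome are undefined, and the default analysis does not test the stated hypothesis. This is more than a missing detail, because the default can give a wrong answer. On signed Z, a convergence of 30% is found 5% to 25% of the time for starting means from 0 to +0.5, against 59% to 66% on |Z|. The false-success result is conditional on lower Z counting as success and on a starting mean below about +0.2. The stated power cannot be carried over to a distance response: under the same correlation and standardized effect it is about .57 to .65. All of these figures rest on normal Z with SD 1 and equally spaced visits; the |Z| power also takes a mean Z of 0.

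**What to change.** In Sections 2.1 and 6.3 and the matching Synopsis entries, define the primary response as |weight-for-length Z|, with lower values better, and account for baseline |Z| in the planned mixed model. Report signed Z as supportive so that the direction of movement is visible. Squared deviation would also serve if it is prespecified.

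In Sections 2.2 and 6.3, state that the intake response is absolute deviation from estimated requirement, for example |log(intake/requirement)|, with the signed ratio as supportive.

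In Section 6.4, name the response to which the .4 SD applies and restate the power, or justify a different effect size or correlation for |Z|.

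If the sponsor in fact means lower Z, reword the hypothesis to say so and keep the signed response.

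The change needs wording and two derived variables, with no new data collection. The real cost is statistical: at 40 dyads per arm the sponsor must either accept power of about .57 to .65 for 0.4 SD of |Z| or plan for 73 to 90 per arm.
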